7.1 Multi-center Studies

Data will be gathered on all patients in the study concerning their index and follow-up hospitalizations for acute myocardial infarction, stroke, repeat unplanned coronary revascularization, and stent thrombosis. All hospitalizations will be assigned a DRG based on these diagnoses. When a hospitalization includes more than one event, the highest paying DRG will be used. Total hospitalization costs and hospitalization costs after the index hospitalization will be totaled. The difference in

mean hospital costs by treatment are will be assessed and the 95% CI (confidence interval) assessed by bootstrap analysis.

Data will be gathered on all patients in the study that meet the inclusion criteria in between January 1ST, 2010 to June 30TH, 2013.

Each center will provide events according to the following rules:

- Patient level data. In case of a subject undergoing multiple procedures within the time frame of the study we will abstract relevant clinical, demographic and procedural details from the first procedure only
- In case of multiple events of a given type only the first event will be reported for purposes of survival analyses.

Detailed technical instructions will be provided to each site in order to extract the relevant data from each database prior to exporting to the data coordinating center.

8 Summary of Study Data

All summary tables will be organized in columns for each treatment (Prasugrel/Clopidogrel) and overall and will be annotated with the total population size relevant to that table/treatment, including any missing observations.

Total, mean, SD (standard deviation), median, min, and max will be specified for continuous data frequency and percentage (based on the non-missing sample size) of observed levels will be reported for all categorical data.

8.1 Demographic and Baseline Variables

For each center the variables listed in the table in the section 12 Listing of Tables, Listings, and Figures will be considered as demographic or baseline variables.

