Propensity scores will be calculated using a multivariable logistic regression model with the dependent outcome as treatment initiation with prasugrel (versus clopidogrel). In addition to age, and gender, this model will include all baseline covariates demonstrating significant differences ($p < 0.05$) between groups. Additional variables for which there is consensus that may be related to either the outcome or exposure will also be included as covariates, even in the absence of significant baseline differences between groups. From this logistic regression model, each observation will be assigned a predicted probability for prasugrel treatment. Baseline characteristics including calculated propensity score will be reviewed to better understand the data and specified analyses plan for the outcomes (stratification, matching, IPW, and etc) will be finalized and documented prior to any actual analyses on the outcomes. The distribution of propensity scores for the entire cohort and each treatment group will be visually examined. Mutually exclusive strata will then be generated based on the propensity scores for the entire cohort, a process which will be blinded to any outcome data in order to avoid bias in selection. The number of strata and their respective cut-points will not be defined *a priori* but will be based on fulfilling the following criteria:

1. Sufficient number of strata to ensure adequate bias adjustment (i.e. at least 5 strata) [Rosenbaum et al., 1984];
2. Sufficient proportion of prasugrel and clopidogrel patients (at least 3%) within each stratum to allow reliable risk estimation [D'Agostino et al., circulation 2007];
3. Adequate balance in baseline covariates will be assessed by calculating the standardized differences between exposure groups within strata for the following variables: age, gender, serum creatinine, serum hemoglobin and prevalence of DM. A standardized difference exceeding 10% will be considered as inadequate bias adjustment..
4. Individuals with an extremely high or low propensity for prasugrel, defined as propensity scores exceeding the 95th or below the 5th percentile for the

entire cohort, may be removed from the analysis of the primary MACE endpoint (i.e. trimming).

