The adjusted associations between exposure groups and the primary MACE outcome will then be calculated using Cox proportional hazards regression. This model will include the following two covariates: exposure group (prasugrel versus clopidogrel) and study center, with propensity group entered as a stratification variable.

The following sensitivity analyses for the primary MACE outcome will also be performed:

1. Covariate adjustment. Hazard ratios for the primary MACE outcome associated with prasugrel versus clopidogrel treatment will be generated using a fully-fitted Cox proportional hazards regression model. In addition to age, , gender and study center, this model will include all baseline covariates demonstrating significant differences ($p < 0.05$) between groups. Other baseline variables that may be plausibly related to the primary outcome will also be included: BMI, race, diabetes mellitus, serum creatinine, hemoglobin, prior MI, prior CHF, prior PAD, prior cerebrovascular disease, multivessel disease, CAD presentation (unstable angina vs. nstemi vs. stemi), current smoking, number of stents implanted, stent type and stent diameter (maximum). A second covariate-adjusted model will be generated using forward stepwise regression with treatment forced in first.

2. Propensity matching: A 1:1 matched cohort will be derived from the overall sample using the propensity scores as described above. Matches will be generated using nearest neighbour matching without replacement (Austin 2011).

3. Equipoise Analysis: From the overall cohort, an 'equipoise' subgroup will be derived that includes all patients with preference scores ranging between 0.4 – 0.6. These patients are assumed to have a reasonable high probability of being assigned to either treatment (Walker et al., 2013).

4. Inverse Probability Weight Analysis: Inverse probability weights (IPW) will be derived for all observations using the propensity scores. Observations with propensity scores exceeding the 95th percentile or below the 5th percentile for the

entire cohort will be excluded (trimmed) for purposes of this specific analysis. After trimming regression analyses will be performed using these weights.

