The following tables will be used to derive from an accompanying data set or spreadsheet that will be used to automate the aesthetic aspects of table production.

Table Listings

Number	Table Title	Summary Statistics	Formal Analysis
1	Summary of Baseline Characteristics by therapy at PCI	n, mean, SD, Median, min, max, n (%)	χ^2 test or Fisher's exact test will be performed for categorical variables as necessary and independent sample t-test continuous variables
2	Summary of Procedural Characteristics by therapy at PCI	n, mean, SD, Median, min, max, n (%)	χ^2 test or Fisher's exact test will be performed for categorical variables as necessary and independent sample t-test continuous variables
3	Procedural Events	n (%)	χ^2 test test for proportion
4	Clinical Outcomes by therapy at PCI	KM estimation [95% CI], crude HR, Propensity-adjusted HR; Covariate-adjusted HR	log-rank test, Cox model
5	Economic Outcomes by Discharge Therapy	mean, SD, Median, min, max, 95% CI for continuous variables, n (%)	t-tests, exact tests, and/or nonparametric tests; bootstrapping; GLM for continuous variables
		KM estimation [95% CI], crude HR, HR propensity score adjusted	χ^2 test, fishers exact test, KM estimation, log rank test, Cox model for categorical variables

Figure Listings

	Title	outcome	Pop	Type of graph	Horizontal Variables	Vertical Variables	Groupings	Statistics	Facets
1	KM rates at 90 days	MACE	Full Analysis	KM	time	probability		KM Estimates	NA
1a	KM rates by Therapy at PCI at 90 days	MACE	Full Analysis	KM	time	probability	Treatment	KM Estimates	NA
2	KM rates at 1 year	MACE	Full Analysis	KM	time	probability		KM Estimates	NA
2a	KM rates by Therapy at PCI at 1 year	MACE	Full Analysis	KM	time	probability	Treatment	KM Estimates	NA

The corresponding Mock Tables are in the following section.

Table 1. Summary of Baseline Characteristics by Therapy at PCI.

	Overall (N = XX)	Prasugrel XX (XX%)	Clopidogrel XX (XX%)	Pvalue
DEMOGRAPHICS				
Age, years				x.xxx
N, N Missing	xxx,x	xxx,x	xxx,x	
Mean ± Std	x.xx ± x.xx	x.xx ± x.xx	x.xx ± x.xx	
Median	x.xx	x.xx	x.xx	
Min , Max	x.xx,x.xx	x.xx,x.xx	x.xx,x.xx	
Gender (female)	xx (x.x%)	xx (x.x%)	xx (x.x%)	x.xxx
Height (cm)				x.xxx
N, N Missing	xxx,x	xxx,x	xxx,x	
Mean ± Std	x.xx ± x.xx	x.xx ± x.xx	x.xx ± x.xx	
Median	x.xx	x.xx	x.xx	
Min , Max	x.xx,x.xx	x.xx,x.xx	x.xx,x.xx	
Weight (Kg)				x.xxx
N, N Missing	xxx,x	xxx,x	xxx,x	
Mean ± Std	x.xx ± x.xx	x.xx ± x.xx	x.xx ± x.xx	
Median	x.xx	x.xx	x.xx	

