Min , Max	x.xx,x.xx	x.xx,x.xx	x.xx,x.xx	
Ethnicity		xx (x.x%)	xx (x.x%)	x.xxx
Hispanic	xx (x.x%)	xx (x.x%)	xx (x.x%)	
Non-Hispanic	xx (x.x%)	xx (x.x%)	xx (x.x%)	
Race				
African American	xx (x.x%)	xx (x.x%)	xx (x.x%)	x.xxx
White	xx (x.x%)	xx (x.x%)	xx (x.x%)	x.xxx
Other	xx (x.x%)	xx (x.x%)	xx (x.x%)	x.xxx
Diabetes at baseline	xx (x.x%)	xx (x.x%)	xx (x.x%)	x.xxx
Insulin-requiring diabetes at baseline	xx (x.x%)	xx (x.x%)	xx (x.x%)	x.xxx
Hypertension	xx (x.x%)	xx (x.x%)	xx (x.x%)	x.xxx
Hypercholesterolemia	xx (x.x%)	xx (x.x%)	xx (x.x%)	x.xxx
Pre-Procedure Creatinine, mg/dl				x.xxx
N, N Missing	xxx,x	xxx,x	xxx,x	
Mean ± Std	x.xx ± x.xx	x.xx ± x.xx	x.xx ± x.xx	
Median	x.xx	x.xx	x.xx	
Min , Max	x.xx,x.xx	x.xx,x.xx	x.xx,x.xx	
Pre-Procedure Hemoglobin, mg/dl				x.xxx
N, N Missing	xxx,x	xxx,x	xxx,x	

Table 1. Summary of Baseline Characteristics by Therapy at PCI.

	Overall (N = XX)	Prasugrel XX (XX%)	Clopidogrel XX (XX%)	Pvalue
Mean ± Std	x.xx ± x.xx	x.xx ± x.xx	x.xx ± x.xx	
Median	x.xx	x.xx	x.xx	
Min , Max	x.xx,x.xx	x.xx,x.xx	x.xx,x.xx	
Troponin				x.xxx
N, N Missing	xxx,x	xxx,x	xxx,x	
Mean ± Std	x.xx ± x.xx	x.xx ± x.xx	x.xx ± x.xx	
Median	x.xx	x.xx	x.xx	
Min , Max	x.xx,x.xx	x.xx,x.xx	x.xx,x.xx	
Baseline CK-MB, ng/ml				x.xxx
N, N Missing	xxx,x	xxx,x	xxx,x	
Mean ± Std	x.xx ± x.xx	x.xx ± x.xx	x.xx ± x.xx	
Median	x.xx	x.xx	x.xx	
Min , Max	x.xx,x.xx	x.xx,x.xx	x.xx,x.xx	
Peak serum creatinine, mg/dl				x.xxx
N, N Missing	xxx,x	xxx,x	xxx,x	
Mean ± Std	x.xx ± x.xx	x.xx ± x.xx	x.xx ± x.xx	
Median	x.xx	x.xx	x.xx	
Min , Max	x.xx,x.xx	x.xx,x.xx	x.xx,x.xx	
Nadir hemoglobin, g/dl (lowest within 72 hours)				x.xxx
N, N Missing	xxx,x	xxx,x	xxx,x	
Mean ± Std	x.xx ± x.xx	x.xx ± x.xx	x.xx ± x.xx	
Median	x.xx	x.xx	x.xx	
Min , Max	x.xx,x.xx	x.xx,x.xx	x.xx,x.xx	
Peak CK-MB, ng/ml (highest 6-24 hours after PCI)				x.xxx
N, N Missing	xxx,x	xxx,x	xxx,x	
Mean ± Std	x.xx ± x.xx	x.xx ± x.xx	x.xx ± x.xx	
Median	x.xx	x.xx	x.xx	
Min , Max	x.xx,x.xx	x.xx,x.xx	x.xx,x.xx	
Peak Troponin (highest 6-24 hours after PCI)				x.xxx
N, N Missing	xxx,x	xxx,x	xxx,x	
Mean ± Std	x.xx ± x.xx	x.xx ± x.xx	x.xx ± x.xx	
Median	x.xx	x.xx	x.xx	
Min , Max	x.xx,x.xx	x.xx,x.xx	x.xx,x.xx	
Smoking	xx (x.x%)	xx (x.x%)	xx (x.x%)	x.xxx
ISCHEMIC HISTORY				
Family history of CAD	xx (x.x%)	xx (x.x%)	xx (x.x%)	x.xxx
Previous MI	xx (x.x%)	xx (x.x%)	xx (x.x%)	x.xxx
Previous PCI	xx (x.x%)	xx (x.x%)	xx (x.x%)	x.xxx

Table 1. Summary of Baseline Characteristics by Therapy at PCI.

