	Overall (N = XX)	Prasugrel XX (XX%)	Clopidogrel XX (XX%)	Pvalue
Previous CABG	xx (x.x%)	xx (x.x%)	xx (x.x%)	x.xxx
Prior CHF	xx (x.x%)	xx (x.x%)	xx (x.x%)	x.xxx
Prior PAD	xx (x.x%)	xx (x.x%)	xx (x.x%)	x.xxx
Prior Cerebrovascular Disease	xx (x.x%)	xx (x.x%)	xx (x.x%)	x.xxx
Left ventricular ejection fraction (%)				x.xxx
N, N Missing	xxx,x	xxx,x	xxx,x	
Mean ± Std	x.xx ± x.xx	x.xx ± x.xx	x.xx ± x.xx	
Median	x.xx	x.xx	x.xx	
Min , Max	x.xx,x.xx	x.xx,x.xx	x.xx,x.xx	
CAD Presentation	xx (x.x%)	xx (x.x%)	xx (x.x%)	x.xxx
Non-ST-elevation myocardial infarction	xx (x.x%)	xx (x.x%)	xx (x.x%)	
ST-elevation myocardial infarction	xx (x.x%)	xx (x.x%)	xx (x.x%)	
Unstable Angina	xx (x.x%)	xx (x.x%)	xx (x.x%)	
PCI status	xx (x.x%)	xx (x.x%)	xx (x.x%)	x.xxx
PCI Indication	xx (x.x%)	xx (x.x%)	xx (x.x%)	x.xxx
Stress or Imaging pre procedure	xx (x.x%)	xx (x.x%)	xx (x.x%)	x.xxx
MEDICATIONS AT ADMISSION				
Beta Blocker	xx (x.x%)	xx (x.x%)	xx (x.x%)	x.xxx
Ca Channel Blocker	xx (x.x%)	xx (x.x%)	xx (x.x%)	x.xxx
Aspirin	xx (x.x%)	xx (x.x%)	xx (x.x%)	x.xxx
Clopidogrel	xx (x.x%)	xx (x.x%)	xx (x.x%)	x.xxx
Prasugrel	xx (x.x%)	xx (x.x%)	xx (x.x%)	x.xxx
Ticagrelor	xx (x.x%)	xx (x.x%)	xx (x.x%)	x.xxx
Nitrate	xx (x.x%)	xx (x.x%)	xx (x.x%)	x.xxx
Ranexa	xx (x.x%)	xx (x.x%)	xx (x.x%)	x.xxx
MEDICATIONS AT DISCHARGE				
ACE-I or ARB	xx (x.x%)	xx (x.x%)	xx (x.x%)	x.xxx
Aspirin	xx (x.x%)	xx (x.x%)	xx (x.x%)	x.xxx
Beta Blocker	xx (x.x%)	xx (x.x%)	xx (x.x%)	x.xxx
Statin	xx (x.x%)	xx (x.x%)	xx (x.x%)	x.xxx
Clopidogrel	xx (x.x%)	xx (x.x%)	xx (x.x%)	x.xxx
75 mg	xx (x.x%)	xx (x.x%)	xx (x.x%)	x.xxx
150 mg	xx (x.x%)	xx (x.x%)	xx (x.x%)	x.xxx
Prasugrel	xx (x.x%)	xx (x.x%)	xx (x.x%)	x.xxx
5 mg	xx (x.x%)	xx (x.x%)	xx (x.x%)	x.xxx
10 mg	xx (x.x%)	xx (x.x%)	xx (x.x%)	x.xxx
Anticoagulant	xx (x.x%)	xx (x.x%)	xx (x.x%)	x.xxx

Table 2. Summary of Procedural Characteristics by Discharge Therapy.

	Overall (N = XX)	Prasugrel XX (XX%)	Clopidogrel XX (XX%)	Pvalue
PROCEDURAL MEDICATIONS				
Aspirin	xx (x.x%)	xx (x.x%)	xx (x.x%)	x.xxx
Fondaparinux	xx (x.x%)	xx (x.x%)	xx (x.x%)	x.xxx
LMWH	xx (x.x%)	xx (x.x%)	xx (x.x%)	x.xxx
UFH	xx (x.x%)	xx (x.x%)	xx (x.x%)	x.xxx
Bivalirudin	xx (x.x%)	xx (x.x%)	xx (x.x%)	x.xxx
IIb/IIIa	xx (x.x%)	xx (x.x%)	xx (x.x%)	x.xxx
Clopidogrel	xx (x.x%)	xx (x.x%)	xx (x.x%)	x.xxx
Prasugrel	xx (x.x%)	xx (x.x%)	xx (x.x%)	x.xxx
ANGIOGRAPHIC CHARACTERISTICS				
Multivessel disease	xx (x.x%)	xx (x.x%)	xx (x.x%)	x.xxx
Total stent length				x.xxx
N, N Missing	xxx,x	xxx,x	xxx,x	

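### SAP 8.1, Table 1 and the p<0.05 rule together make post-PCI laboratory values and discharge drugs eligible for the propensity score

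*SAP*

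**What the plan says.** - **Exposure and clock.** SAP 6.1 assigns patients by the drug received at the time of PCI, whatever they are given at discharge. SAP 4.3 and 6.1 count follow-up and the 90-day endpoint from the index PCI.
- **What counts as baseline.** SAP 8.1: "the variables listed in the table in the section 12 Listing of Tables, Listings, and Figures will be considered as demographic or baseline variables".
- **What the table holds.** The first table in SAP Section 12 is listed as "Summary of Baseline Characteristics by therapy at PCI". Next to the pre-procedure creatinine and hemoglobin rows it has peak serum creatinine, "Nadir hemoglobin, g/dl (lowest within 72 hours"), "Peak CK-MB, ng/ml (highest 6-24 hours after PCI") and "Peak Troponin (highest 6-24 hours after PCI"). It also has a block headed "MEDICATIONS AT DISCHARGE", which includes clopidogrel and prasugrel by dose.
- **What enters the score.** Of the propensity model, SAP 6.1 says that "this model will include all baseline covariates demonstrating significant differences", with the threshold at p<0.05. Variables agreed to be related to outcome or exposure are added. No closed list is given, and nothing limits candidates to values known before PCI.
- **Where the score is used.** The primary Cox model contains "exposure group (prasugrel versus clopidogrel) and study center, with propensity group entered as a stratification variable". Matching and inverse probability weighting use the same scores. Sensitivity analysis 1 (covariate adjustment) repeats the p<0.05 rule. Secondary outcomes, bleeding included, use propensity stratification as well.

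**The concern.** A propensity score should hold only variables that treatment cannot have changed. The 6-24 hour peaks and the discharge drugs are recorded after exposure is fixed and after the clock has started. The peak creatinine and nadir hemoglobin rows stand apart from the pre-procedure values of the same tests.

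Three things are at stake.

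- **Near-copy of exposure.** The discharge drug largely repeats the drug given at PCI. Stratifying on it leaves few patients on the minority drug in each stratum. A switch before discharge may itself follow an in-hospital event. Patients who die in hospital have no discharge prescription, so the field would be imputed under SAP 6.6 or coded as no, and outcome information would leak into the score.
- **Bleeding.** Nadir hemoglobin over 72 hours is in part a result of bleeding. Attachment 1 defines the post-procedure bleeding field over 72 hours too. Conditioning on the nadir could mask a bleeding difference.
- **Shared fault.** SAP 6.7 calls the additional analyses confirmatory. Matching, weighting and covariate adjustment could all carry the same problem, so their agreement with the primary result would be weak reassurance.

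**Working it through.** **1. The plan's own figure.** SAP 6.8 gives 4,303 per arm for 8.0% against a 20% relative reduction (6.4%), 80% power, alpha 0.05 and 10% drop-out. Two-sided alpha is assumed.

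n = [1.96·√(2·0.072·0.928) + 0.8416·√(0.08·0.92 + 0.064·0.936)]² / 0.016² = 4,096 per arm, and 4,096/0.90 = 4,552 after drop-out.

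The 4,303 is not reproduced with full 10% inflation. That is a separate matter. The figure is used here only to size the consequence.

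**2. Would the variables pass p<0.05?** At 4,303 per arm the smallest significant standardized difference is 1.96·√(2/4,303) = 0.042, so trivial differences in a laboratory value qualify.

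For discharge on prasugrel, let s be the share discharged on the other drug, taken as equal in both arms:

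z = (1 − 2s) / √(0.5/4,303) = (1 − 2s)/0.01078

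This gives z = 74 at s = 0.10 and z = 83 at s = 0.05. Entry is near certain for the discharge drugs. For the laboratory values it is plausible but conditional on the data.

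**3. Loss of information.** Expected events after drop-out: 8,606 × 0.90 × (0.080 + 0.064)/2 = 558. If the score contains the discharge drug, the within-stratum split approaches s : (1 − s). Then

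- information relative to 1:1 = 4s(1 − s)
- power = Φ(√[558·s(1 − s)]·|ln 0.80| − 1.96)

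| s (assumed) | Information vs 1:1 | Power at HR 0.80 |
|---|---|---|
| 1:1 split (pre-treatment score) | 100% | 75% |
| 0.15 | 51% | 47% |
| 0.10 | 36% | 35% |
| 0.05 | 19% | 21% |

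The documents do not give s. The nearest figures are for switching by 90 days: at most 10% (SAP 5.1) and less than 15% (protocol 3.4.9). Neither measures PCI-to-discharge change.

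**4. Direction.** In a small simulation with assumed effects, five equal strata and 60 runs per setting, a pre-treatment score gave a hazard ratio of 0.78 (SE 0.085). Adding a post-PCI variable affected by treatment gave 0.84. Adding the discharge drug at 10% discordance gave 1.12 (SE 0.122).

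The last value comes from the five equal strata, because the middle one pairs higher-risk prasugrel patients with lower-risk clopidogrel patients. With six or ten strata the same set-up returns to about 0.80, with precision still poor. The SAP leaves the number of strata and the cut-points open. The simulation also let discharge drug depend only on drug at PCI, so it omits bias from switching after in-hospital events. It shows that direction is not fixed in advance; it is not a forecast.

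**The case against.** The strongest reply is that this rule is assembled and not stated. SAP 8.1 sits under a heading about data summaries, and neither 8.1 nor 6.1 refers to the other. SAP 8.3 places discharge drugs in a class of their own. The creatinine and hemoglobin named in 6.1 are defined in Attachment 1 as pre-procedure values, and no peak, nadir or discharge variable is named there. SAP 6.1 also requires baseline characteristics and score distributions to be examined, and the analysis plan finalized, before outcomes are analysed. A score containing the discharge drug would look nearly separated.

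Much of this stands as evidence of intent, and a careful analyst might drop these variables. It does not close the gap:

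- SAP 8.3 adds a second label without taking the drugs out of Table 1.
- The review step is written to choose among stratification, matching and weighting; it does not screen the timing of covariates.
- The balance check covers five variables. A failure would invite new cut-points as readily as removal of a covariate.
- The rule of at least 3% of each drug per stratum can be met once discordance is 3% or more.

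A reader might infer four stronger points that the documents do not support.

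- **That bias must run toward the null.** Step 4 shows that it need not.
- **That the primary hazard ratio is adjusted for part of its own endpoint.** This depends on whether in-hospital post-procedure MI counts in MACE. The Table 4 footnote and the Attachment 1 MI field define MI by hospitalization, while SAP 6.1 includes index-hospital events and 4.3 cites the universal definition. The question is open.
- **That in-hospital events are baseline too.** Reading 8.1 as all of Section 12 would add Table 3. The singular wording does not require that.
- **That leaving study center and calendar time out of the score is an error.** Center is in the primary Cox model, and the clause in 6.1 on agreed additional variables can admit both.

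**Conclusion.** The point holds as a defect in the text of the SAP. Applied literally, 8.1, Table 1 and 6.1 let post-treatment variables into the propensity score and the covariate-adjusted Cox model, and nothing in the plan rules them out. It should be fixed before the score is built, because it decides what the primary hazard ratio estimates.

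Entry is near certain for the discharge study drugs and likely but not assured for the laboratory values. The loss of power rests on three assumptions: the SAP's event rates, 10% of patients lost, and a PCI-to-discharge discordance that the documents do not report. The size and sign of any bias cannot be stated in advance. The effect on bleeding through nadir hemoglobin is a possibility, not a computed quantity.

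**What to change.** - In SAP 6.1 and 8.1, limit candidates for the propensity score and for covariate adjustment to values fixed before the index PCI, and list them. Apply the same limit to the variables added by consensus.
- Exclude by name peak creatinine, nadir hemoglobin, peak CK-MB, peak troponin and all discharge medications.
- Move those rows from Table 1 to a separate descriptive table of post-PCI values.
- State in 6.1 that the matched, equipoise and weighted analyses use the restricted score.

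The cost is SAP wording and a rearranged table shell, with no new data. As an optional refinement, study center and calendar quarter of the index PCI could be named in the propensity model. The PCI date is a listed data field, and center is already used in the Cox model.

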8.2 Concurrent Illnesses and Medical Conditions

Concurrent Illnesses and Medical Conditions will be collected as baseline Variables according to the table section 12 Listing of Tables, Listings, and Figures.

The following tables will be used to derive from an accompanying data set or spreadsheet that will be used to automate the aesthetic aspects of table production.

Table Listings

Number	Table Title	Summary Statistics	Formal Analysis
1	Summary of Baseline Characteristics by therapy at PCI	n, mean, SD, Median, min, max, n (%)	χ^2 test or Fisher's exact test will be performed for categorical variables as necessary and independent sample t-test continuous variables
2	Summary of Procedural Characteristics by therapy at PCI	n, mean, SD, Median, min, max, n (%)	χ^2 test or Fisher's exact test will be performed for categorical variables as necessary and independent sample t-test continuous variables
3	Procedural Events	n (%)	χ^2 test test for proportion
4	Clinical Outcomes by therapy at PCI	KM estimation [95% CI], crude HR, Propensity-adjusted HR; Covariate-adjusted HR	log-rank test, Cox model
5	Economic Outcomes by Discharge Therapy	mean, SD, Median, min, max, 95% CI for continuous variables, n (%)	t-tests, exact tests, and/or nonparametric tests; bootstrapping; GLM for continuous variables
		KM estimation [95% CI], crude HR, HR propensity score adjusted	χ^2 test, fishers exact test, KM estimation, log rank test, Cox model for categorical variables

Figure Listings

	Title	outcome	Pop	Type of graph	Horizontal Variables	Vertical Variables	Groupings	Statistics	Facets
1	KM rates at 90 days	MACE	Full Analysis	KM	time	probability		KM Estimates	NA
1a	KM rates by Therapy at PCI at 90 days	MACE	Full Analysis	KM	time	probability	Treatment	KM Estimates	NA
2	KM rates at 1 year	MACE	Full Analysis	KM	time	probability		KM Estimates	NA
2a	KM rates by Therapy at PCI at 1 year	MACE	Full Analysis	KM	time	probability	Treatment	KM Estimates	NA

The corresponding Mock Tables are in the following section.

Table 1. Summary of Baseline Characteristics by Therapy at PCI.

	Overall (N = XX)	Prasugrel XX (XX%)	Clopidogrel XX (XX%)	Pvalue
DEMOGRAPHICS				
Age, years				x.xxx
N, N Missing	xxx,x	xxx,x	xxx,x	
Mean ± Std	x.xx ± x.xx	x.xx ± x.xx	x.xx ± x.xx	
Median	x.xx	x.xx	x.xx	
Min , Max	x.xx,x.xx	x.xx,x.xx	x.xx,x.xx	
Gender (female)	xx (x.x%)	xx (x.x%)	xx (x.x%)	x.xxx
Height (cm)				x.xxx
N, N Missing	xxx,x	xxx,x	xxx,x	
Mean ± Std	x.xx ± x.xx	x.xx ± x.xx	x.xx ± x.xx	
Median	x.xx	x.xx	x.xx	
Min , Max	x.xx,x.xx	x.xx,x.xx	x.xx,x.xx	
Weight (Kg)				x.xxx
N, N Missing	xxx,x	xxx,x	xxx,x	
Mean ± Std	x.xx ± x.xx	x.xx ± x.xx	x.xx ± x.xx	
Median	x.xx	x.xx	x.xx	
Min , Max	x.xx,x.xx	x.xx,x.xx	x.xx,x.xx	
Ethnicity		xx (x.x%)	xx (x.x%)	x.xxx
Hispanic	xx (x.x%)	xx (x.x%)	xx (x.x%)	
Non-Hispanic	xx (x.x%)	xx (x.x%)	xx (x.x%)	
Race				
African American	xx (x.x%)	xx (x.x%)	xx (x.x%)	x.xxx
White	xx (x.x%)	xx (x.x%)	xx (x.x%)	x.xxx
Other	xx (x.x%)	xx (x.x%)	xx (x.x%)	x.xxx
Diabetes at baseline	xx (x.x%)	xx (x.x%)	xx (x.x%)	x.xxx
Insulin-requiring diabetes at baseline	xx (x.x%)	xx (x.x%)	xx (x.x%)	x.xxx
Hypertension	xx (x.x%)	xx (x.x%)	xx (x.x%)	x.xxx
Hypercholesterolemia	xx (x.x%)	xx (x.x%)	xx (x.x%)	x.xxx
Pre-Procedure Creatinine, mg/dl				x.xxx
N, N Missing	xxx,x	xxx,x	xxx,x	
Mean ± Std	x.xx ± x.xx	x.xx ± x.xx	x.xx ± x.xx	
Median	x.xx	x.xx	x.xx	
Min , Max	x.xx,x.xx	x.xx,x.xx	x.xx,x.xx	
Pre-Procedure Hemoglobin, mg/dl				x.xxx
N, N Missing	xxx,x	xxx,x	xxx,x	

Table 1. Summary of Baseline Characteristics by Therapy at PCI.

	Overall (N = XX)	Prasugrel XX (XX%)	Clopidogrel XX (XX%)	Pvalue
Mean ± Std	x.xx ± x.xx	x.xx ± x.xx	x.xx ± x.xx	
Median	x.xx	x.xx	x.xx	
Min , Max	x.xx,x.xx	x.xx,x.xx	x.xx,x.xx	
Troponin				x.xxx
N, N Missing	xxx,x	xxx,x	xxx,x	
Mean ± Std	x.xx ± x.xx	x.xx ± x.xx	x.xx ± x.xx	
Median	x.xx	x.xx	x.xx	
Min , Max	x.xx,x.xx	x.xx,x.xx	x.xx,x.xx	
Baseline CK-MB, ng/ml				x.xxx
N, N Missing	xxx,x	xxx,x	xxx,x	
Mean ± Std	x.xx ± x.xx	x.xx ± x.xx	x.xx ± x.xx	
Median	x.xx	x.xx	x.xx	
Min , Max	x.xx,x.xx	x.xx,x.xx	x.xx,x.xx	
Peak serum creatinine, mg/dl				x.xxx
N, N Missing	xxx,x	xxx,x	xxx,x	
Mean ± Std	x.xx ± x.xx	x.xx ± x.xx	x.xx ± x.xx	
Median	x.xx	x.xx	x.xx	
Min , Max	x.xx,x.xx	x.xx,x.xx	x.xx,x.xx	
Nadir hemoglobin, g/dl (lowest within 72 hours)				x.xxx
N, N Missing	xxx,x	xxx,x	xxx,x	
Mean ± Std	x.xx ± x.xx	x.xx ± x.xx	x.xx ± x.xx	
Median	x.xx	x.xx	x.xx	
Min , Max	x.xx,x.xx	x.xx,x.xx	x.xx,x.xx	
Peak CK-MB, ng/ml (highest 6-24 hours after PCI)				x.xxx
N, N Missing	xxx,x	xxx,x	xxx,x	
Mean ± Std	x.xx ± x.xx	x.xx ± x.xx	x.xx ± x.xx	
Median	x.xx	x.xx	x.xx	
Min , Max	x.xx,x.xx	x.xx,x.xx	x.xx,x.xx	
Peak Troponin (highest 6-24 hours after PCI)				x.xxx
N, N Missing	xxx,x	xxx,x	xxx,x	
Mean ± Std	x.xx ± x.xx	x.xx ± x.xx	x.xx ± x.xx	
Median	x.xx	x.xx	x.xx	
Min , Max	x.xx,x.xx	x.xx,x.xx	x.xx,x.xx	
Smoking	xx (x.x%)	xx (x.x%)	xx (x.x%)	x.xxx
ISCHEMIC HISTORY				
Family history of CAD	xx (x.x%)	xx (x.x%)	xx (x.x%)	x.xxx
Previous MI	xx (x.x%)	xx (x.x%)	xx (x.x%)	x.xxx
Previous PCI	xx (x.x%)	xx (x.x%)	xx (x.x%)	x.xxx

Table 1. Summary of Baseline Characteristics by Therapy at PCI.

	Overall (N = XX)	Prasugrel XX (XX%)	Clopidogrel XX (XX%)	Pvalue
Previous CABG	xx (x.x%)	xx (x.x%)	xx (x.x%)	x.xxx
Prior CHF	xx (x.x%)	xx (x.x%)	xx (x.x%)	x.xxx
Prior PAD	xx (x.x%)	xx (x.x%)	xx (x.x%)	x.xxx
Prior Cerebrovascular Disease	xx (x.x%)	xx (x.x%)	xx (x.x%)	x.xxx
Left ventricular ejection fraction (%)				x.xxx
N, N Missing	xxx,x	xxx,x	xxx,x	
Mean ± Std	x.xx ± x.xx	x.xx ± x.xx	x.xx ± x.xx	
Median	x.xx	x.xx	x.xx	
Min , Max	x.xx,x.xx	x.xx,x.xx	x.xx,x.xx	
CAD Presentation	xx (x.x%)	xx (x.x%)	xx (x.x%)	x.xxx
Non-ST-elevation myocardial infarction	xx (x.x%)	xx (x.x%)	xx (x.x%)	
ST-elevation myocardial infarction	xx (x.x%)	xx (x.x%)	xx (x.x%)	
Unstable Angina	xx (x.x%)	xx (x.x%)	xx (x.x%)	
PCI status	xx (x.x%)	xx (x.x%)	xx (x.x%)	x.xxx
PCI Indication	xx (x.x%)	xx (x.x%)	xx (x.x%)	x.xxx
Stress or Imaging pre procedure	xx (x.x%)	xx (x.x%)	xx (x.x%)	x.xxx
MEDICATIONS AT ADMISSION				
Beta Blocker	xx (x.x%)	xx (x.x%)	xx (x.x%)	x.xxx
Ca Channel Blocker	xx (x.x%)	xx (x.x%)	xx (x.x%)	x.xxx
Aspirin	xx (x.x%)	xx (x.x%)	xx (x.x%)	x.xxx
Clopidogrel	xx (x.x%)	xx (x.x%)	xx (x.x%)	x.xxx
Prasugrel	xx (x.x%)	xx (x.x%)	xx (x.x%)	x.xxx
Ticagrelor	xx (x.x%)	xx (x.x%)	xx (x.x%)	x.xxx
Nitrate	xx (x.x%)	xx (x.x%)	xx (x.x%)	x.xxx
Ranexa	xx (x.x%)	xx (x.x%)	xx (x.x%)	x.xxx
MEDICATIONS AT DISCHARGE				
ACE-I or ARB	xx (x.x%)	xx (x.x%)	xx (x.x%)	x.xxx
Aspirin	xx (x.x%)	xx (x.x%)	xx (x.x%)	x.xxx
Beta Blocker	xx (x.x%)	xx (x.x%)	xx (x.x%)	x.xxx
Statin	xx (x.x%)	xx (x.x%)	xx (x.x%)	x.xxx
Clopidogrel	xx (x.x%)	xx (x.x%)	xx (x.x%)	x.xxx
75 mg	xx (x.x%)	xx (x.x%)	xx (x.x%)	x.xxx
150 mg	xx (x.x%)	xx (x.x%)	xx (x.x%)	x.xxx
Prasugrel	xx (x.x%)	xx (x.x%)	xx (x.x%)	x.xxx
5 mg	xx (x.x%)	xx (x.x%)	xx (x.x%)	x.xxx
10 mg	xx (x.x%)	xx (x.x%)	xx (x.x%)	x.xxx
Anticoagulant	xx (x.x%)	xx (x.x%)	xx (x.x%)	x.xxx

Table 2. Summary of Procedural Characteristics by Discharge Therapy.

	Overall (N = XX)	Prasugrel XX (XX%)	Clopidogrel XX (XX%)	Pvalue
PROCEDURAL MEDICATIONS				
Aspirin	xx (x.x%)	xx (x.x%)	xx (x.x%)	x.xxx
Fondaparinux	xx (x.x%)	xx (x.x%)	xx (x.x%)	x.xxx
LMWH	xx (x.x%)	xx (x.x%)	xx (x.x%)	x.xxx
UFH	xx (x.x%)	xx (x.x%)	xx (x.x%)	x.xxx
Bivalirudin	xx (x.x%)	xx (x.x%)	xx (x.x%)	x.xxx
IIb/IIIa	xx (x.x%)	xx (x.x%)	xx (x.x%)	x.xxx
Clopidogrel	xx (x.x%)	xx (x.x%)	xx (x.x%)	x.xxx
Prasugrel	xx (x.x%)	xx (x.x%)	xx (x.x%)	x.xxx
ANGIOGRAPHIC CHARACTERISTICS				
Multivessel disease	xx (x.x%)	xx (x.x%)	xx (x.x%)	x.xxx
Total stent length				x.xxx
N, N Missing	xxx,x	xxx,x	xxx,x	
Mean ± Std	x.xx ± x.xx	x.xx ± x.xx	x.xx ± x.xx	
Median	x.xx	x.xx	x.xx	
Min , Max	x.xx,x.xx	x.xx,x.xx	x.xx,x.xx	
At least 1 type B2/C lesion	xx (x.x%)	xx (x.x%)	xx (x.x%)	x.xxx
At least 1 lesion with moderate/severe calcifications	xx (x.x%)	xx (x.x%)	xx (x.x%)	x.xxx
At least 1 bifurcation lesion	xx (x.x%)	xx (x.x%)	xx (x.x%)	x.xxx
At least one bare metal stent	xx (x.x%)	xx (x.x%)	xx (x.x%)	x.xxx
At least one drug eluting stent (1st gen)	xx (x.x%)	xx (x.x%)	xx (x.x%)	x.xxx
At least one drug eluting stent (2 nd gen)	xx (x.x%)	xx (x.x%)	xx (x.x%)	x.xxx
PCI vessel LM	xx (x.x%)	xx (x.x%)	xx (x.x%)	x.xxx
PCI vessel LAD	xx (x.x%)	xx (x.x%)	xx (x.x%)	x.xxx
PCI vessel LCx	xx (x.x%)	xx (x.x%)	xx (x.x%)	x.xxx
PCI vessel RCA	xx (x.x%)	xx (x.x%)	xx (x.x%)	x.xxx

Table 3. In-Hospital Post-Procedural Events by Therapy at PCI.

	Overall (N=XX)	Prasugrel XX (XX%)	Clopidogrel XX (XX%)	Pvalue
MI	xx (x.x%)	xx (x.x%)	xx (x.x%)	x.xxx
Cardiogenic Shock	xx (x.x%)	xx (x.x%)	xx (x.x%)	x.xxx
Heart Failure	xx (x.x%)	xx (x.x%)	xx (x.x%)	x.xxx
CVA/Stroke	xx (x.x%)	xx (x.x%)	xx (x.x%)	x.xxx
Tamponade	xx (x.x%)	xx (x.x%)	xx (x.x%)	x.xxx
Dialysis	xx (x.x%)	xx (x.x%)	xx (x.x%)	x.xxx
Vascular Complication	xx (x.x%)	xx (x.x%)	xx (x.x%)	x.xxx
Blood Transfusion	xx (x.x%)	xx (x.x%)	xx (x.x%)	x.xxx
Bleeding event (72 hours)	xx (x.x%)	xx (x.x%)	xx (x.x%)	x.xxx

Table 4 In and Out of Hospital Post-Procedural Events by Therapy at PCI.

	Clopidogrel	Prasugrel	Unadjusted HR [95% CI]	Propensity adjusted HR [95% CI]	Covariate-adjusted HR [95% CI]
MACE ¹					
90 Day	x.xx% [x.xx%-x.xx%]	x.xx% [x.xx%-x.xx%]	x.xx [x.xx-x.xx]	x.xx [x.xx-x.xx]	x.xx [x.xx-x.xx]
1 Year	x.xx% [x.xx%-x.xx%]	x.xx% [x.xx%-x.xx%]	x.xx [x.xx-x.xx]	x.xx [x.xx-x.xx]	x.xx [x.xx-x.xx]
Death					
90 Day	x.xx% [x.xx%-x.xx%]	x.xx% [x.xx%-x.xx%]	x.xx [x.xx-x.xx]	x.xx [x.xx-x.xx]	x.xx [x.xx-x.xx]
1 Year	x.xx% [x.xx%-x.xx%]	x.xx% [x.xx%-x.xx%]	x.xx [x.xx-x.xx]	x.xx [x.xx-x.xx]	x.xx [x.xx-x.xx]
Myocardial infarction					
90 Day	x.xx% [x.xx%-x.xx%]	x.xx% [x.xx%-x.xx%]	x.xx [x.xx-x.xx]	x.xx [x.xx-x.xx]	x.xx [x.xx-x.xx]
1 Year	x.xx% [x.xx%-x.xx%]	x.xx% [x.xx%-x.xx%]	x.xx [x.xx-x.xx]	x.xx [x.xx-x.xx]	x.xx [x.xx-x.xx]
Unplanned Revascularization					
90 Day	x.xx% [x.xx%-x.xx%]	x.xx% [x.xx%-x.xx%]	x.xx [x.xx-x.xx]	x.xx [x.xx-x.xx]	x.xx [x.xx-x.xx]
1 Year	x.xx% [x.xx%-x.xx%]	x.xx% [x.xx%-x.xx%]	x.xx [x.xx-x.xx]	x.xx [x.xx-x.xx]	x.xx [x.xx-x.xx]
Bleeding					
90 Day	x.xx% [x.xx%-x.xx%]	x.xx% [x.xx%-x.xx%]	x.xx [x.xx-x.xx]	x.xx [x.xx-x.xx]	x.xx [x.xx-x.xx]
1 Year	x.xx% [x.xx%-x.xx%]	x.xx% [x.xx%-x.xx%]	x.xx [x.xx-x.xx]	x.xx [x.xx-x.xx]	x.xx [x.xx-x.xx]
Stroke					
90 Day	x.xx% [x.xx%-x.xx%]	x.xx% [x.xx%-x.xx%]	x.xx [x.xx-x.xx]	x.xx [x.xx-x.xx]	x.xx [x.xx-x.xx]
1 Year	x.xx% [x.xx%-x.xx%]	x.xx% [x.xx%-x.xx%]	x.xx [x.xx-x.xx]	x.xx [x.xx-x.xx]	x.xx [x.xx-x.xx]

Table 4 In and Out of Hospital Post-Procedural Events by Therapy at PCI.

	Clopidogrel	Prasugrel	Unadjusted HR [95% CI]	Propensity adjusted HR [95% CI]	Covariate-adjusted HR [95% CI]
Def/Probable Stent Thrombosis					
90 Day	x.xx% [x.xx%-x.xx%]	x.xx% [x.xx%-x.xx%]	x.xx [x.xx-x.xx]	x.xx [x.xx-x.xx]	x.xx [x.xx-x.xx]
1 Year	x.xx% [x.xx%-x.xx%]	x.xx% [x.xx%-x.xx%]	x.xx [x.xx-x.xx]	x.xx [x.xx-x.xx]	x.xx [x.xx-x.xx]

¹MACE is defined as all cause death, hospitalization for myocardial infarction, stroke, or unplanned revascularization. ²HR calculated from propensity stratified model. ³HR calculated multivariable-adjusted model.

Table 6. Healthcare Utilization and Costs by Therapy at Discharge

	Overall (N = XX)	Prasugrel XX (XX%)	Clopidogrel XX (XX%)	Pvalue
Index Hospital Length of Stay				
N, N Missing	xxx,x	xxx,x	xxx,x	
Mean ± Std	x.xx ± x.xx	x.xx ± x.xx	x.xx ± x.xx	
Median	x.xx	x.xx	x.xx	
Min , Max	x.xx,x.xx	x.xx,x.xx	x.xx,x.xx	
Index Hospital Total Costs				
N, N Missing	xxx,x	xxx,x	xxx,x	
Mean ± Std	x.xx ± x.xx	x.xx ± x.xx	x.xx ± x.xx	
Median	x.xx	x.xx	x.xx	
Min , Max	x.xx,x.xx	x.xx,x.xx	x.xx,x.xx	

Table 6. Healthcare Utilization and Costs by Therapy at Discharge

	Overall (N = XX)	Prasugrel XX (XX%)	Clopidogrel XX (XX%)	Pvalue
30 day Rehospitalization Total Costs				
N, N Missing	xxx,x	xxx,x	xxx,x	
Mean ± Std	x.xx ± x.xx	x.xx ± x.xx	x.xx ± x.xx	
Median	x.xx	x.xx	x.xx	
Min , Max	x.xx,x.xx	x.xx,x.xx	x.xx,x.xx	
90 day Rehospitalization Total Costs				
N, N Missing	xxx,x	xxx,x	xxx,x	
Mean ± Std	x.xx ± x.xx	x.xx ± x.xx	x.xx ± x.xx	
Median	x.xx	x.xx	x.xx	
Min , Max	x.xx,x.xx	x.xx,x.xx	x.xx,x.xx	
180 day Rehospitalization Total Costs				
N, N Missing	xxx,x	xxx,x	xxx,x	
Mean ± Std	x.xx ± x.xx	x.xx ± x.xx	x.xx ± x.xx	
Median	x.xx	x.xx	x.xx	
Min , Max	x.xx,x.xx	x.xx,x.xx	x.xx,x.xx	
1yr Rehospitalization Total Costs				
N, N Missing	xxx,x	xxx,x	xxx,x	
Mean ± Std	x.xx ± x.xx	x.xx ± x.xx	x.xx ± x.xx	
Median	x.xx	x.xx	x.xx	
Min , Max	x.xx,x.xx	x.xx,x.xx	x.xx,x.xx	
1yr Aggregate (Index + Rehospitalization) Total Costs				
N, N Missing	xxx,x	xxx,x	xxx,x	

Table 6. Healthcare Utilization and Costs by Therapy at Discharge

	Overall (N = XX)	Prasugrel XX (XX%)	Clopidogrel XX (XX%)	Pvalue
Mean ± Std	x.xx ± x.xx	x.xx ± x.xx	x.xx ± x.xx	
Median	x.xx	x.xx	x.xx	
Min , Max	x.xx,x.xx	x.xx,x.xx	x.xx,x.xx	

13 Attachment 1. Data Fields and Descriptions/Definitions

	VALUE	Description/Definition
Patient ID	#####	Patient ID for terms of this dataset (assigned after data consolidation, deidentified)
Date of Index PCI	DDMMYYYY	Actual date of procedure
Date of admission	DDMMYYYY	Actual date of admission associated with index event
Date of discharge	DDMMYYYY	Actual date of discharge associated with index event
Date of birth	DDMMYYYY	Date patient was born
Gender	0= male, 1= female	Indicate patient's gender
Weight (Kg)	## in Kilograms	Indicate the patient's weight in kilograms
Height (cm)	### in cms	Indicate patient's height in cm
Hispanic	0=no, 1=yes	Hispanic or Latino Ethnicity: A person of Cuban, Mexican, Puerto Rican, Cuban, South or Central American, or other Spanish culture or origin, regardless of race. The term, "Spanish origin," can be used in addition to "Hispanic or Latino."
Black/African American	0=no, 1=yes	Black/African American (Race): Having origins in any of the black racial groups of Africa. Terms such as "Haitian" or "Negro" can be used in addition to "Black or African American."
White	0=no, 1=yes	White (Race): Having origins in any of the original peoples of Europe, the Middle East, or North Africa
Diabetes at baseline	0=no, 1=yes	Indicate if the patient has a history of diabetes mellitus regardless of duration of disease or need for antidiabetic agents. Supporting Definitions: Diabetes Mellitus: Diabetes mellitus is diagnosed by a physician or can be defined as a fasting blood sugar greater than 7 mmol/l or 126 mg/dL. It does not include gestational diabetes.

Insulin-requiring diabetes at baseline	0=no, 1=yes	Indicate if patient currently using insulin (Y/N) Target Value: The value on arrival at this facility Selections: Supporting Definitions: (none) Note(s): Patients placed on a pre-procedure diabetic pathway of insulin drip after arrival but were not on insulin therapy (treated by diet or oral method) are not coded as insulin treatment. If a patient had a pancreatic transplant, code "other", since the insulin from the new pancreas is not exogenous insulin.
